# 1 Study Summary

Title	Rapid initiation of buprenorphine/naloxone to optimize MAT utilization in Philadelphia		
Short Title	Rapid initiation of BUP/NX		
Study overview	The proposed research will evaluate the ability of a mobile, rapid induction procedure to engage individuals in ongoing medication assisted treatment. A total of 250 untreated ndividuals meeting criteria for opioid use disorder and at high risk of opioid overdose will be enrolled in the study. Recruitment will take place in two targeted neighborhoods of Philadelphia (Kensington and South Philadelphia) with a high prevalence of fatal and non- fatal opioid overdose. A total of 250 participants will be engaged in the research. Following nformed consent and determination of eligibility, 125 individuals will be enrolled as they engage with the mobile, rapid induction team and 125 individuals will be enrolled as they seek treatment from the CRC Episcopal Hospital (serving Kensington area) or BAC/CRC Hall Mercer Community Mental Health (serving South Philadelphia). The intervention group will receive four weeks of treatment with buprenorphine /naloxone and support for treatment engagement provided by a case manager and a peer recovery specialist. All participants will be assessed at baseline and then 1- and 6-month following enrollment. The primary endpoint for the study is continued enrollment in medication-assisted treatment at 6 months post enrollment.		
Study Duration	The estimated duration of study is 36 months. Individual study subject participation will last 6 months.		
Study Center(s)	The University of Pennsylvania will serve as the primary project location, and all recruitment and data collection efforts will be executed by University of Pennsylvania staff members. A subcontract has been established with Prevention Point Philadelphia and Public Health Management Corporation.		
Objectives	
 
The proposed research will evaluate the ability of a mobile, rapid induction procedure to engage individuals in ongoing medication assisted treatment.
 
The specific aims are: 
 
Aim 1: To evaluate the impact of the mobile, transitional MAT intervention on its ability to engage participants in targeted, existing MAT treatment slots at 1- and 6-month post-enrollment.
 
Aim 2: To evaluate the impact of the mobile intervention on subsequent drug use and overdoses at 6-month post-enrollment.
 
Aim 3: To assess the acceptability and costs of the intervention. We will document the program and patient costs of delivering and participating in the intervention.
 
 
 
		
Number of Subjects	A total of 250 participants will be engaged in the research at the time they seek treatment: 125 individuals will be enrolled as they engage with the mobile, rapid induction team and 125 individuals will be enrolled as they seek treatment from the BAC/CRC (treatment as usual).		

	Inclusion Criteria:					
	Must be 18 years of age or older					
	Opioid overdose in the prior 12 months					
	Meet criteria for opioid use disorder					
Main Inclusion	Resident of Philadelphia					
Willingness and ability to participate in study procedures						
and Exclusion	Exclusion Criteria:					
Criteria	
 
Inability to comprehend or complete study procedures
 
					
	Plans to relocate during study time frame					
	
 
Diagnosis of serious liver disease (LFT >3x normal ranges)
 
					
	Currently in medication assisted treatment (MAT) for substance use disorder					
	Pregnancy or lactation					
	Moderate to severe alcohol or benzodiazepine use disorder					
	• The intervention consists in a rapid initiation of buprenorphine/naloxone, counseling,					
	peer support and case management as a method for linkage to long-term, evidence-					
	based medication assisted treatment.					
	• Inductions will be initiated in the individual's home community, either on our mobile					
	medical facility or via home visits.					
	• The mobile team will be led by a nurse practitioner (able to prescribe					
Intervention	buprenorphine/haloxone in PA) and include a peer recovery specialist (PRS), and a					
Intervention	case manager. The team will rapidly commin opioid use disorder and fisk of overdose,					
	month) course of huprepornational paloyone treatment. During this time, the dedicated					
	case manager and PRS will work with the participants to belo them become engaged					
	in existing medication assisted treatment programs					
	• The type of ongoing treatment will be determined on an individual basis and will					
	include options of methadone maintenance, buprenorphine/naloxone treatment, or					
	extended-release naltrexone (XR-NTX).					
	Comparison on engagement rates in ongoing opiate use disorder treatment at the					
	two time points (1- and 6-months) using a repeated measures logistic regression					
	model, incorporating the propensity score (to correct for non-randomized trial)					
	Evaluate the change in substance use and severity of addiction using a repeated					
	measures model to compare the groups on the ASI drug composite score at months					
	1 and 6.					
Statistical	Compare of the number of overdoses per participant between groups using repeated					
Mothodology	measures Poisson regression models, if there is sufficient variability in the number of					
wethodology	Poisson model, we will classify participants as baying no overdoses versus at least					
	one and compare the groups using repeated measures logistic regression models					
	
 
Evaluation of the sensitivity of our main analyses to the presence of missing data by
 
					
	performing a sensitivity analysis, in which we will obtain estimates of the group effect					
	under various non-ignorability assumptions, using selection models to examine the					
	effects of missing data, using logistic regression models, and incorporate the					
	predicted probabilities into a weighted analysis of the main hypotheses.					
	The study will be monitored by the PIs and co-investigators, and Philadelphia Department					
Data and Safat	of Public Health Institutional Review Board, as well as by regulatory committees at the					
Data and Salety	University of Pennsylvania (i.e., IRBs, OHR) and Center for Studies of Addiction Data Safety					
Monitoring Plan	Monitoring Board (Penn DSMB). During the course of the study, safety and data quality					
	monitoring will be performed on an ongoing basis by the Principal Investigator and the study					
	staff.					

The information that follows constitutes the research protocol for the Rapid initiation of buprenorphine/naloxone to

optimize MAT utilization in Philadelphia study. This study will be conducted in compliance with the provisions set forth in this document. This study will also be conducted in full accordance with all applicable University of Pennsylvania Research Policies and Procedures, Good Clinical Practice Standards and all applicable Federal and state laws and regulations including 45 CFR 46, 21 CFR Parts 50, 54, 56. All episodes of noncompliance will be documented.

The proposed research will test a mobile intervention designed to initiate treatment and link individuals with opioid use disorder and a high risk of overdose to ongoing medication-assisted treatment (MAT). Despite the high prevalence of opioid use disorder and elevated rate of fatal and non-fatal overdose in Philadelphia, over 20% of MAT capacity goes unused. The proposed intervention will rapidly initiate treatment with buprenorphine/naloxone and provide one-month of medication coverage, peer support and case management sharply focused on linkage to ongoing MAT (i.e., methadone, buprenorphine/naloxone, extended-release naltrexone). Several critical barriers to treatment (stigma, time, and distance) will be minimized by rapidly initiating MAT in the individual's home environment.

In 2016, a total of 63,632 Americans died of a drug overdose and opioids were involved in 66.4% of these cases (42,249 overdose deaths) (Seth, Scholl et al. 2018). At present, opioid-related overdoses are the leading cause of accidental death in the country with a mortality rate that has guadrupled since 2000 and increased by 44.1% from 2015. In Pennsylvania, between July 2016 and September 2017, the CDC Enhanced State Opioid Overdose Surveillance system reported an 81% increase of the ED visits for suspected opioid overdoses. Statewide, there were 4,627 overdose deaths in 2016, an increase of 44.1% from 2015, the second highest rate of increase of any state during this reporting period (Centers for Disease Control and Prevention 2018). In Philadelphia, in 2017 there were 1,217 drug overdose deaths. Medical examiner reports indicate that 88% involved opioids, including prescription opioids, heroin, and fentanyl (City of Philadelphia, 2018). The increasing presence of fentanyl is directly associated with the escalating numbers of fatalities and in 2017, fentanyl was found in over 80% of the opioid fatalities. The 2017 the age-adjusted opioid-related death rate (59.8 per 100,000) was more than twice that found in New York City and greater than any of the other largest cities in the country. Conservative estimates suggest that there are 70,000 individuals using heroin in Philadelphia and approximately, 50,000 who misuse opioid prescription medications. According to the DEA, the heroin sold in Philadelphia has the highest purity and the lowest price in the country. A bag of heroin in Philadelphia is now cheaper than a pack of cigarettes. Philadelphia is an urban epicenter of the opioid epidemic in the United States.

There is no demographic that remains unaffected by the opioid crisis in Philadelphia (City of Philadelphia, 2018). The age adjusted mortality rates have increased for all categories of age, race and gender. The highest rates of increase over the past two years have occurred for women (49% increase) and 15 to 24-year old (62% increase). Using the City of Philadelphia Department of Health and Human Services' integrated data system (CARES), analyses of fatal overdoses during the past 5 years indicated that 70% were males, 63% white, and 27% were ages 25 to 34. Importantly, 41.4% of these individuals had contact with at least one service of the Philadelphia Behavioral Health System within the 6 months of their death and 26.4% within 1 month of their death.

Geographically, the opioid epidemic has affected all neighborhoods in the City. Of relevance to this application, the two areas of highest concentration for fatal overdoses are the Kensington and South Philadelphia. These are the target areas for the proposed intervention. It is also important to note that nearly 75% of fatal overdoses took place in private residences. The proposed intervention will be accessible to those with stabile as well as unstable housing.

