# 5.2 Sample Size and Power Determination

Our power analysis has been based on this primary aim. Our primary hypothesis is that participants who received rapid induction will more likely be engaged in ongoing treatment at 1- and 6-month follow-up than participants who sought treatment at BAC/CRC. We will test this hypothesis at a 5% level of significance. Our principal interest is in the comparison of engagement rates between the mobile intervention and BAC/CRC groups, at months 1 and 6. Preliminary data suggest an engagement rate of about 20-30% in the BAC/CRC group. Assuming a steady loss to attrition that yields 80% completers, and a within-subject correlation of 0.3, the methods of Diggle et al. (Diggle, Heagerty et al. 2002) show that our sample size of 125 in each group yields 80% power for differences of about 15% in engagement rates between the two groups (e.g., 80% power for BAC/CRC: 25% vs. Mobile: 40%, corresponding to a RR=1.6 and an OR=2.0)

**Propensity score model to account for non-randomized allocation:** The participants are not randomly assigned to the mobile rapid induction intervention and BAC/CRC groups, so it is possible that there will be confounding of the group effect with the effects of characteristics of the participants. We will use a propensity score approach (Rosenbaum 2002, Rothman, Greenland et al. 2008) to account for this. We will use a broad range of baseline variables as covariates in a logistic regression model predicting treatment group, including age, race/ethnicity, gender, number of previous overdoses, number of previous treatments for opiate use disorder, type of opioid used, and depression. The model will yield predicted probabilities of BAC/CRC group for all participants (the propensity score), and we will create a five-level ordinal variable based on the quintiles of the propensity score. We will then include this ordinal variable as a stratum variable in our models.

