**Analyses for the primary aim:** i.e. to evaluate the impact of the mobile, transitional MAT intervention on its ability to engage participants in targeted, existing MAT treatment slots at 1- and 6-month post-enrollment. For each of the 1- and 6-month time points, we will classify participants as being engaged/not-engaged (where non-engaged will include dropped out or missing). We will compare the groups on engagement rates at the two time points using a repeated measures logistic regression model, incorporating the propensity score as described above (Diggle, Heagerty et al. 2002). The fixed effects will be binary indicators of treatment group and time point; we will test for a group by time interaction to assess whether the group effect differs at month 1 and month 6. As there are only two time points, we will use an unstructured covariance matrix to accommodate within-participant covariance.

**Analyses for Aim 2:** We will also use a repeated measures model to compare the groups on the ASI drug composite score at months 1 and 6. The model will be similar to that described for the engagement analyses of Aim 1, but with a beta distribution assumed for the response, to accommodate the bounded range (zero to one) of the ASI composite scores. We will compare the groups on the number of overdoses per patient using repeated measures Poisson regression models, if there is sufficient variability in the number of overdoses reported. If a low rate of overdoses causes convergence issues for the Poisson model, we will classify participants as having no overdoses versus at least one, and compare the groups using repeated measures logistic regression models.

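### Adjusting only for propensity-score fifths leaves a small, avoidable part of the measured confounding in the group comparison

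*Combined protocol and SAP*

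**What the plan says.** Section 1 (Study Summary, Statistical Methodology) gives the purpose of the score in a parenthesis: the engagement analysis is a repeated measures logistic "model, incorporating the propensity score (to correct for non-randomized trial"). It does not say in what form the score is used.

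Section 5.2 does. In the paragraph on the propensity score, a logistic model predicts treatment group from baseline variables such as age, gender, previous overdoses, previous treatments and depression. Then "we will create a five-level ordinal variable based on the quintiles of the propensity score", and "We will then include this ordinal variable as a stratum variable in our models". Whether the five levels enter as indicators or as a linear trend is not stated.

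In the primary-aim paragraph, "We will compare the groups on engagement rates at the two time points using a repeated measures logistic regression model" with the score included in that form. The fixed effects named there are group and time, with a test of their interaction. The Aim 2 model for the ASI drug composite is described as similar. The plan has no balance check within fifths and no sensitivity analysis with the uncut score.

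**The concern.** Allocation is by self-selection, and the propensity score is the plan's only stated protection for the main comparison. Cutting a continuous score into five groups discards the differences inside each group. Someone near the top of a fifth is more likely to be in one arm than someone near the bottom, so the arms remain unbalanced within every fifth, in the same direction each time. With no other baseline covariate in the outcome model, nothing removes this remainder.

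With five fixed groups the remainder does not shrink as the sample grows. If measured characteristics favor the mobile group, it pushes the engagement odds ratio upward and adds some false positive conclusions. If they favor BAC/CRC, it works the other way.

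**Working it through.** **1. The plan's own figure.** Inputs from section 5.2: "our sample size of 125 in each group yields 80% power for differences of about 15% in engagement rates"; "80% power for BAC/CRC: 25% vs. Mobile: 40%, corresponding to a RR=1.6 and an OR=2.0"; "Assuming a steady loss to attrition that yields 80% completers, and a within-subject correlation of 0.3"; "We will test this hypothesis at a 5% level of significance". Two-sided testing is assumed.

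- Completers per arm: 125 × 0.80 = 100. With two visits, effective n = 100 × 2 / (1 + 0.3) = 153.8.
- z = [0.15 × √153.8 − 1.96 × √(2 × 0.325 × 0.675)] / √(0.25 × 0.75 + 0.40 × 0.60) = (1.861 − 1.298) / 0.654 = 0.86, so power is 0.805.
- Odds ratio = (0.40/0.60) / (0.25/0.75) = 2.0, log odds ratio 0.69. Relative risk = 0.40/0.25 = 1.6.

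The stated 80% reproduces. It contains no term for the propensity score, so it serves only as a yardstick.

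**2. Imbalance left inside fifths, large sample.** Share left = (weighted mean of the within-fifth arm differences in the logit score) / (overall arm difference). For an assumed standard deviation of the score logit between 0.4 and 1.5, the share is 8% to 10%.

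**3. Planned model, simulated.** Set-up: 125 per arm, 7 covariates, logistic propensity model, two correlated visits, robust standard errors, no true effect. Confounding strengths and outcome shapes are assumptions. Over the scenarios with crude bias, quintile strata left 3% to 29% of the crude log odds ratio bias, mostly 5% to 15%. The remainder was 0.01 to 0.08, with standard errors of 0.23 to 0.27.

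**4. Strata alone against strata plus the logit score** (1,500 runs per scenario, Monte Carlo error 0.006 to 0.007; bias in log odds ratio):

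| Assumed scenario | Crude | Quintiles | Quintiles + logit | SD, quintiles / combined |
|---|---|---|---|---|
| Moderate, linear | 0.34 | 0.044 (13%) | 0.013 (4%) | 0.241 / 0.241 |
| Strong, linear | 0.57 | 0.045 (8%) | −0.002 (0%) | 0.271 / 0.273 |
| Moderate, skewed and curved | 0.38 | 0.047 (12%) | −0.010 (−3%) | 0.245 / 0.248 |
| Strong, skewed and curved | 0.65 | 0.075 (12%) | −0.008 (−1%) | 0.273 / 0.275 |
| Strong, curved | 0.61 | 0.057 (9%) | −0.001 (0%) | 0.256 / 0.259 |

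False significant results favoring the mobile group fell from 3.2–5.3% to 1.9–3.1% (nominal 2.5%). A separate set of runs agreed: 0.016 to 0.062 left by quintiles (5% to 12%), −0.006 to +0.004 by the combined model, SD at most about 2% larger, and false positives down from 3.1–4.8% to 2.2–2.9%.

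**5. Gain in total error.** Root mean squared error = √(bias² + SD²). Fourth row: √(0.075² + 0.273²) = 0.283 against √(0.008² + 0.275²) = 0.275, a fall of about 3%. Third row: 0.2495 against 0.2482, about 0.5%.

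**6. The linear logit score without strata** (2,500 runs per scenario, skewed covariates):

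| Outcome shape | Quintiles | Logit score alone |
|---|---|---|
| U-shaped | 0.084 (29%) | −0.086 (−30%) |
| Levelling off | 0.011 (4.5%) | 0.031 (13%) |
| Step | 0.006 (3%) | 0.025 (11%) |

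Replacing the strata by a linear logit term can therefore do no better than quintiles, or worse.

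**The case against.** The strongest reply is that this is a choice between acceptable methods. Quintile stratification is declared openly and removes most of the measured confounding. What it leaves is small: two-sided type I error was 0.045 to 0.067 with quintiles and 0.041 to 0.064 with the uncut probability score, against 0.11 to 0.57 unadjusted in the scenarios with crude bias. All of this stands, and it makes the point a minor one.

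A reader might infer that the Study Summary contradicts section 5.2, because it speaks of correcting for non-randomization. It does not. The parenthesis states a purpose and promises no complete removal of bias; section 5.2 is merely more specific.

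A reader might also infer that the uncut score would simply remove the remainder at no cost in precision. That fails as a general statement, as step 6 shows. Against the five-level version, the variance with an uncut score ranged from 15% lower to 4% higher.

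Nor is the combined model perfect. In one further scenario, on the risk-difference scale, a residual of +0.43 percentage points became −0.26 with a Monte Carlo error of 0.08, a slight overcorrection. What survives is that the combined model consistently left less bias, at almost no cost.

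**Conclusion.** The point holds as a small, inexpensive improvement. Under plausible but assumed confounding, stratifying on fifths alone leaves about 5% to 15% of the crude bias, or 0.02 to 0.08 in log odds ratio. A true odds ratio of 1 would appear as about 1.02 to 1.08 (e^0.02 to e^0.08). At most this is 0.08/0.25, about a third of a standard error, and 0.08/0.69, about 12% of the planned effect.

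The documents give neither strength nor direction of confounding, so these sizes are illustrations. They do not support calling the primary analysis invalid. Nor does a better use of the score settle the comparability of the arms. Participants reach the mobile team through advertising and word of mouth (section 3.5.1), and whatever part of that selection the measured covariates miss is untouched by any form of the score.

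**What to change.** In section 5.2, propensity score paragraph, keep the quintile strata, state that they enter as indicators, and add one sentence: the logit of the estimated propensity score is also included as a continuous covariate in the Aim 1 and Aim 2 models. The logit term should accompany the strata, not replace them, because the strata absorb curvature that a single linear term misses. Also specify that standardized differences of the baseline covariates within strata are examined before any outcome data are analyzed. The Study Summary needs no change.

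The cost is one degree of freedom, a standard deviation about 0% to 2% larger, and no additional data. The change should be fixed before outcomes are seen.

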#### 2.1 Responses to the epidemic

Beginning in the mid 1970's, efforts directed at reducing the problems associated with drug use were led by the criminal justice systems. The United States' "War on Drugs" resulted in changes in law and enforcement policies leading to almost 3% of the US adult population being under some form of criminal justice supervision by the early 2000's (Peters, Young et al. 2017). These policies created a system of mass incarceration and relied on ineffective abstinence-only approaches, resulting in harmful consequences and in huge economic and human costs (Belenko, Hiller et al. 2013). One of the consequences of these failed policies has been the neglect of evidence-based treatment approaches and systems.

Rapid initiation of BUP/NX Version 1: Nov-15-2018

Scientific and medical communities have advocated for increasing the availability of evidence-based pharmacotherapeutic approaches (Volkow, Frieden et al. 2014, Blum, Gold et al. 2016). In 2017, the US Department of Health and Human Services declared a public health emergency and announced a 5-point strategy to combat the opioid crisis. The strategy included improving access to evidence-based treatment and recovery services, promoting use of naloxone to prevent overdose, strengthening the understanding of the epidemic through better public health surveillance, providing support for cutting edge research on pain and addiction, and advancing better practices for pain management (US Department of Health and Human Services 2018). The opioid epidemic is a complex public health issue that should be addressed with multifaceted approaches including harm reduction and evidence-based treatment of the opioid addiction.

An important response to the opioid epidemic in Philadelphia has been the rapid scale up of naloxone access and training. When administered correctly and in time, can prevent death from opioid overdose. Different approaches for naloxone deliveries have been extensively examined and have concluded in the efficacy of the widespread coverage of naloxone to reduce overdose (Rowe, Santos et al. 2015, Kirane, Ketteringham et al. 2016, Wagner, Bovet et al. 2016, Fairbairn, Coffin et al. 2017, Faulkner-Gurstein 2017). In Philadelphia, naloxone has become widely available and has been used to reverse over 7,000 overdoses in 2017.

Although an effective tool for fatal overdose prevention, naloxone is not a treatment of opioid addiction or a prevention for future overdose. In fact, a recent publication showed that non-fatal overdose is the highest risk factor for subsequent fatal overdose (Caudarella, Dong et al. 2016). Consistent with these findings, the above map displaying the incidence of naloxone use is nearly identical to the one displaying the incidence of fatal overdose in Philadelphia. These findings support the importance of linking individuals to effective opioid addiction treatment after an overdose.

